#### **10.3.2.2 Assessment of Shift from Baseline in Clinical Laboratory Variables**

The baseline and post-baseline laboratory observations will be categorized as Grade 1, Grade 2, Grade 3, and Grade 4 according to OMERACT criteria (Rheumatology Common Toxicity Criteria v.2.0). For creatine phosphokinase and creatinine, NCI CTC criteria will be used.

For each laboratory variable, shift tables will be generated that cross tabulate the subjects as deemed appropriate by "as treated" treatment group:

- Category of the baseline value versus category of the final value.
- Category of the baseline value versus maximum category.
- Category of the baseline value versus minimum category.

Note that the minimum/maximum category is used, rather than the category of the minimum/maximum value. The two may be different due to variation in the reference range.

No statistical tests will be performed for this analysis.

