### **10.3 Analysis of Laboratory Data**

#### **10.3.1 Variables and Units**

All laboratory parameters to be collected in this study are listed below. Laboratory parameters will be reported using the standard international (SI) units.

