### **10.3.2.3 Assessment of Potentially Clinical Significant Laboratory Values**

The criteria for potentially clinically significant laboratory values will be determined by OMERACT criteria of Grade 3 or 4. For creatine phosphokinase and creatinine, NCI CTC criteria will be used.

The number and percentage of subjects meeting the criteria for potentially clinically significant laboratory values will be summarized by "as treated" treatment group and overall. Comparisons of the percentage of subjects experiencing a value meeting the criteria between treatment groups will be performed using Fisher's exact tests. Only p-values  $\leq 0.100$  when rounded to three digits will be presented.

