### **10.3.3.2 Assessment of Potentially Clinically Significant Laboratory Values**

Long-term laboratory data will be summarized based on the number and percentage of subjects meeting the criteria for potentially clinically significant laboratory values and by the actual treatment received at the time of the event occurrence. Starting with Amendment 4, all subjects will receive open-label upadacitinib 15 mg QD, including those currently on upadacitinib 30 mg QD. The treatment groups for summarizing potentially clinically significant laboratory values are the same as the ones for long-term AE analysis as described in Section 8.1 and Section 10.2.2. A subject can be counted under different treatment groups if he/she switched treatment and experienced potentially clinically significant laboratory values under different treatment groups.

In the evaluation of potentially clinically significant laboratory values, the baseline value will be determined by the last non-missing measurement recorded on or before the date of the first dose of study drug in the corresponding treatment group (which may be different than the first dose of study drug received in the study). For example, for a subject who started on Placebo and switched to Upadacitinib 15 mg QD, lab values under Upadacitinib 15 mg QD exposure would be evaluated against the baseline value defined as the last non-missing measurement recorded on or before the date of the first dose of Upadacitinib 15 mg QD. For subjects who switched from upadacitinib 30 mg QD to upadacitinib 15 mg QD, lab values under upadacitinib 15 mg QD exposure would still be evaluated against the baseline defined based on the first dose of Upadacitinib 30 mg QD.

A listing of all subjects with any laboratory determination meeting OMERACT criteria of Grade 3 or 4 will be provided by Grade. For creatine phosphokinase and creatinine, NCI CTC criteria will be used. For each of these subjects, the whole course of the respective parameter will be listed.

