J2. Cough	Transient, intermittent, occasional OTC meds relieve	Persistent, requires narcotic or other prescription meds for relief	Recurrent, persistent coughing spasms without consistent relief by meds, interferes with function	Interferes with oxygenation; debilitating
J3. Dyspnea	Subjective, transient, no interference with function	Symptomatic, intermittent or recurring, interferes with exertional activities	Symptomatic during daily routine activities, interferes with function, treatment with intermittent nasal O 2 relieves	Symptomatic at rest, debilitating, requires constant nasal O 2
J4. Pleuritic pain (pleurisy)	Transient, intermittent symptoms, no treatment or OTC meds relieve	Persistent symptoms, requires prescription meds for relief	Prolonged symptoms, interferes with function, requires frequent narcotic pain relief	Debilitation, requiring hospitalisation
J5. Pneumonitis (pulmonary infiltrates)	Asymptomatic radiographic changes, transient, no treatment required	Symptomatic, persistent, requiring corticosteroids	Symptomatic, requiring treatment including O 2	Debilitating, not reversible; or requiring assisted ventilation

J6. Pulmonary function decreased (FVC or carbon monoxide diffusion capacity – DLCO)	76% – 90% of pre-treatment value	51% – 75% of pre-treatment value	26% – 50% of pre-treatment value	≤ 25% of pre-treatment value
Laboratory Data				
K. Haematology				
K1. Hgb (g/dl) decrease from pre-treatment	1.0 – 1.4	1.5 – 2.0	2.1 – 2.9, or Hgb < 8.0, > 7.0	≥ 3.0; or Hgb < 7.0
K2. Leukopenia (total WBC) × 1000	3.0 – 3.9	2.0 – 2.9	1.0 – 1.9	< 1.0
K3. Neutropenia (× 1000)	1.5 – 1.9	1.0 – 1.4	0.5 – 0.9	< 0.5
K4. Lymphopenia (× 1000)	1.5 – 1.9	1.0 – 1.4	0.5 – 0.9	< 0.5
K5. Platelets (× 1000)	75 – LLN	50 – 74.9	20 – 49.9; platelet transfusion required	< 20; recurrent platelet transfusions
L. Chemistry				
L1. Hypercalcaemia (mg/dl)	1.1 × ULN – 11.5	11.6 – 12.5	12.6 – 13.5; or symptoms present	> 13.5; or associated coma
L2. Hyperglycemia (mg/dl) Fasting	140 – 160	161 – 250	251 – 500	> 500, or associated with ketoacidosis
L3. Hyperkalaemia (mmol/l)***	5.5 – 5.9	6.0 – 6.4	6.5 – 7.0 or any ECG change	> 7.0 or any arrhythmia

L5. Hypocalcaemia (mg/dl)	0.9 × LLN – 7.8	7.7 – 7.0	6.9 – 6.5; or associated with symptoms	< 6.5 or occurrence of tetany
L6. Hypoglycemia (mg/dl)	55 – 64 (no symptoms)	40 – 54 (or symptoms present)	30 – 39 (symptoms impair function)	< 30 or coma

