L7. Hyponatraemia (mmol/l)***	-	125 – 129	120 – 124	< 120
L8. Hypokalaemia (mg/dl)***	-	3.0 – 3.4	2.5 – 2.9	< 2.5
L9. CPK (also if polymyositis-disease ****)	1.2 – 1.9 × ULN	2.0 – 4.0 × ULN	4.0 × ULN with weakness but without life-threatening signs or symptoms	> 4.0 × ULN with signs or symptoms of rhabdomyolysis or life-threatening
L10. Serum uric acid	1.2 – 1.6 × ULN	1.7 – 2.9 × ULN	3.0 – 5.0 × ULN or gout	NA
L11. Creatinine (mg/dl) ****	1.1 – 1.3 × ULN	1.4* – 1.8 × ULN	1.9 – 3.0 × ULN	> 3.0 × ULN
L12. SGOT (AST)	1.2 – 1.5 × ULN	1.6 – 3.0 × ULN	3.1 – 8.0 × ULN	> 8.0 × ULN
L13. SGPT (ALT)	1.2 – 1.5 × ULN	1.6 – 3.0 × ULN	3.0 – 8.0 × ULN	> 8.0 × ULN
L14. Alkaline phosphatase	1.1 – 1.5** × ULN	1.6 – 3.0 × ULN	3.0 – 5.0 × ULN	> 5.0 × ULN
L15. T. bilirubin	1.1 – 1.4 × ULN	1.5 – 1.9 × ULN	2.0 – 3.0 × ULN	> 3.0 × ULN
L16. LDH	1.3 – 2.4 × ULN	2.5 – 5.0 × ULN	5.1 – 10 × ULN	> 10 × ULN
M. Urinalysis				
M1. Haematuria	Micro only	Gross, no clots	Clots, transfusion < 2 units	Transfusion required
M2. Proteinuria (per 24 h)	300 – 500 mg (tr/1+)	501 – 1999 mg (2+)	2 – 5.0 g (3+) nephrotic syndrome	5.0 g (4+) anasarca

M3. WBC in urine	NA	NA	Indicating acute interstitial nephritis	Associated with acute renal failure
M4. Uric acid crystals	Present without symptoms	NA	With stones or symptoms of stones (e.g., renal colic)	Causing renal outflow obstruction and hospitalization

\* in L11, 1.5 – 1.8 × ULN is changed to 1.4 – 1.8 × ULN.

\*\* in L14, 1.1 – 2.0 × ULN is changed to 1.1 – 1.5 × ULN.

\*\*\* in L3, L7 and L8, mg/dl is changed to mmol/l.

\*\*\*\*For CPK and Creatinine NCI CTC grading will be used. For CPK therefore the following gradings apply: Grade 1: > ULN – 2.5 × ULN; Grade 2: > 2.5 – 5.0 × ULN; Grade 3: > 5.0 – 10.0 × ULN; Grade 4: > 10.0 × ULN; For Creatinine the following gradings apply: Grade 1: > 1 – 1.5 × Baseline; > ULN – 1.5 × ULN; Grade 2: > 1.5 – 3.0 × Baseline; > 1.5 – 3.0 × ULN; Grade 3: > 3.0 baseline; > 3.0 – 6.0 × ULN; Grade 4: > 6.0 × ULN.

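### SAP Appendix A's laboratory grade bands are not contiguous and no rounding rule is given, so read literally some values at the Grade 3 edge drop out of the potentially clinically significant counts

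*SAP*

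**What the plan says.** SAP 10.3.2.2 states that baseline and post-baseline "laboratory observations will be categorized as Grade 1, Grade 2, Grade 3, and Grade 4 according to OMERACT criteria", with NCI CTC grading for CPK and creatinine. SAP 10.3.2.3 then sets the PCS rule: "The criteria for potentially clinically significant laboratory values will be determined by OMERACT criteria of Grade 3 or 4". At Week 12, comparisons of the resulting percentages "between treatment groups will be performed using Fisher's exact tests". SAP 10.3.3.2 counts subjects meeting the PCS criteria over the long term and adds: "A listing of all subjects with any laboratory determination meeting OMERACT criteria of Grade 3 or 4 will be provided by Grade".

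The bands are in SAP Appendix A. The lymphocyte row reads "K4. Lymphopenia (× 1000) 1.5 – 1.9 1.0 – 1.4 0.5 – 0.9 < 0.5", and the neutrophil row has the same limits. Protocol Appendix Q prints the same haematology limits. On units, SAP 10.3.1 says only: "Laboratory parameters will be reported using the standard international (SI) units". Neither document states the number of decimals or how values are rounded before grading.

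The SAP does amend parts of the table. Its footnotes say "in L11, 1.5 – 1.8 × ULN is changed to 1.4 – 1.8 × ULN", narrow one alkaline phosphatase band (L14), and correct the units of three electrolyte rows. The haematology rows are unchanged. The CPK grading in the same footnotes starts each band strictly above the previous upper limit, so those bands adjoin.

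SAP 11.1 says Period 1 was reported under version 2.0 and that version 3.0 applies only to future long-term reporting.

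**The concern.** The plan promises a grade for every observation, but the printed bands do not cover every value. A count of 0.95 (×1000) has no grade, while the milder 1.2 is Grade 2. Two programmers could drop such a value, round it, or count it as Grade 3, and all would be following the text.

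The stake is the PCS output. Values at the Grade 3 edge decide whether a subject counts as having a PCS result. A literal program omits them from both the long-term percentages and the listing. Gaps between lower grades, such as 1.4 to 1.5 for lymphocytes, cannot change a PCS count. They matter only for shift tables, which the SAP schedules only in its Week 12 section.

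**Working it through.** **Step 1. The bands at the Grade 3 edge (SAP Appendix A).**

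| Row | Grade 2 | Grade 3 | Values without a single grade |
|---|---|---|---|
| Lymphocytes, neutrophils (×1000) | 1.0–1.4 | 0.5–0.9 | between 0.9 and 1.0: none |
| WBC (×1000) | 2.0–2.9 | 1.0–1.9 | between 1.9 and 2.0: none |
| Hgb decrease (g/dL) | 1.5–2.0 | 2.1–2.9 | between 2.0 and 2.1: none |
| AST (× ULN) | 1.6–3.0 | 3.1–8.0 | between 3.0 and 3.1: none |
| Bilirubin (× ULN) | 1.5–1.9 | 2.0–3.0 | between 1.9 and 2.0: none |
| ALT (× ULN) | 1.6–3.0 | 3.0–8.0 | 3.0: two grades |
| Alkaline phosphatase (× ULN) | 1.6–3.0 | 3.0–5.0 | 3.0: two grades |

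An absolute haemoglobin of exactly 7.0 g/dL is in neither the Grade 3 clause (below 8.0, above 7.0) nor the Grade 4 clause (below 7.0). In practice the decrease criterion usually settles it. Screening excludes haemoglobin below 10, and 10.0 − 7.0 = 3.0, which is Grade 4.

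**Step 2. Against the protocol's own levels.** A neutrophil count of 950/µL is 0.95 (×1000). It is below the 1000/µL level in Protocol Table 4 but has no grade. The same holds for a WBC of 1,950/µL against the 2000/µL level.

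**Step 3. Rows in multiples of ULN.** AST/ULN is a calculated ratio, so laboratory decimals do not close its gap. Let the ULN be a whole number u and results be whole units. The gap (3.0u, 3.1u) contains 3u + 1 whenever 3u + 1 < 3.1u, that is, whenever u > 10. So any ULN above 10 U/L leaves some reportable AST result ungraded.

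**Step 4. Size for lymphocytes.** The documents give no lymphocyte distribution and no lymphopenia rate, so there is no planned figure to reproduce. Three readings of Grade 3+ were compared on two-decimal values x:
- contiguous: x < 1.0
- rounded to one decimal: x < 0.95
- literal: x ≤ 0.9

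For single observations under a lognormal with median m and log-SD s, P(x < c) = Φ((ln c − ln m)/s). With m = 1.8 and s = 0.4 (assumed):
- c = 1.0: Φ(−1.469) = 0.0709
- c = 0.95: Φ(−1.598) = 0.0551
- c = 0.9: Φ(−1.733) = 0.0416
- literal/contiguous = 0.0416/0.0709 = 0.59

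The SAP counts subjects with any qualifying value, so this was also simulated per subject. Assumptions: medians 1.4–2.0; between/within-subject log-SD 0.25/0.15, 0.30/0.20 or 0.35/0.25; screening value at least 0.8 (the protocol exclusion limit); 4 or 8 post-baseline draws.

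| Median, log-SD between/within, draws | Contiguous | Rounded | Literal | Literal/contiguous |
|---|---|---|---|---|
| 2.0, 0.25/0.15, 4 | 2.3% | 1.4% | 0.9% | 0.40 (lowest) |
| 1.6, 0.25/0.15, 4 | 11.1% | 7.8% | 5.6% | 0.50 |
| 1.8, 0.30/0.20, 4 | 11.2% | 8.4% | 6.4% | 0.57 |
| 1.6, 0.35/0.25, 4 | 25.4% | 21.1% | 17.8% | 0.70 |
| 1.4, 0.35/0.25, 8 | 46.4% | 40.6% | 35.9% | 0.77 (highest) |

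The literal ratio runs from 0.40 to 0.77, a relative cut of 23–60%. The rounded ratio runs from 0.63 to 0.88, a cut of 12–37%. If counts are reported to one decimal, the three readings coincide.

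**Step 5. Long-term follow-up.** Protocol Appendices D and F give 26 post-baseline haematology draws: 7 in Period 1 (Weeks 2–24), Weeks 36 and 48, 16 from Week 60 to Week 240, and Week 260. With 26 draws, a narrower parameter set (median 1.5–1.9, log-SD 0.30–0.40, within-subject share 30%) gives literal/contiguous ratios of 0.51–0.77, a difference of 5–13 percentage points. Rerunning the Step 4 grid with 26 draws gives 0.46–0.83.

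**The case against.** The best defence is that the table is meant to be read at one decimal. After the SAP edit, the creatinine row (L11) runs 1.1–1.3, 1.4–1.8, 1.9–3.0. Moving 1.5 to 1.4 makes sense only if 1.3 to 1.4 counts as closed. L11 and L14 therefore still have 0.1 steps and are not a precedent for contiguous bands. The protocol's thresholds for these cells are all multiples of 100/µL, so they are no evidence of finer reporting. On that reading the white-cell, neutrophil and lymphocyte rows have no gap.

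This is a reasonable inference about intent, and it is why no effect can be asserted for lymphocytes. But it is not written down, and it does not repair the whole table. Rounding to one decimal turns every ALT ratio from 2.95 up to 3.05 into 3.0, the value with two grades, so it widens that overlap. For AST it moves ratios above 3.0 but below 3.05 into Grade 2, while ALT's Grade 3 begins at 3.0.

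Other limits also stand. Lymphopenia and neutropenia as adverse events of special interest are found by queries of event terms (SAP Table 8), not by grade. Liver elevations have explicit cut-offs (SAP 10.3.2.4 and 10.3.3.3). Mean-change summaries use raw values. The same rule applies in every arm, and no between-arm distortion has been shown. Week 12 is already reported.

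**Conclusion.** The grading rule is defective as printed, but the consequence is confined to laboratory PCS counts and listings and, for lower grades, shift tables. No alpha-controlled endpoint is affected.

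A reader might infer that many values go ungraded and that the Grade 3+ lymphopenia rate roughly halves. The documents do not support that. It needs counts with more than one decimal and a distribution the documents do not give, and it compares the two extreme readings. Halving appears only in the narrower-spread scenarios. With two-decimal counts and the assumed distributions, a fair statement is a 23–60% relative reduction for literal against contiguous bands at 4 or 8 draws, and 12–37% for rounding. At one decimal it is nil for lymphocytes. Nor do the documents show that a treatment-related safety signal is understated.

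For AST the gap exists whatever the laboratory's precision, though the separate count at or above 3 × ULN limits its practical weight. For bilirubin, whether PCS changes depends on which side the gap is closed.

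**What to change.** In SAP Appendix A, for analysis grading only, write half-open adjoining bands in the style already used for CPK:

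- Lymphocytes and neutrophils (×1000): Grade 1 ≥1.5 to <2.0; Grade 2 ≥1.0 to <1.5; Grade 3 ≥0.5 to <1.0; Grade 4 <0.5.
- WBC (×1000): Grade 1 ≥3.0 to <4.0; Grade 2 ≥2.0 to <3.0; Grade 3 ≥1.0 to <2.0; Grade 4 <1.0.
- AST and ALT: Grade 3 >3.0 to 8.0 × ULN, with Grade 2 ending at 3.0.
- Bilirubin, alkaline phosphatase and haemoglobin (decrease, and the value 7.0): the same treatment, saying on which side each limit falls.

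State the laboratory's reporting precision, and that the SAP table governs analysis grading, because Protocol Appendix Q keeps the printed rows. Apply the bands to the remaining long-term PCS tables and listings. State which convention the version 2.0 Week 12 programming used, so that the two sets of grades can be compared. Nothing here changes the protocol's thresholds for managing subjects.

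The cost is a text edit and re-derivation of grades. Grade 3 counts may rise, and if Week 12 was programmed differently, its grades may need re-deriving for consistency.

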### **10.3.2.3 Assessment of Potentially Clinical Significant Laboratory Values**

The criteria for potentially clinically significant laboratory values will be determined by OMERACT criteria of Grade 3 or 4. For creatine phosphokinase and creatinine, NCI CTC criteria will be used.

The number and percentage of subjects meeting the criteria for potentially clinically significant laboratory values will be summarized by "as treated" treatment group and overall. Comparisons of the percentage of subjects experiencing a value meeting the criteria between treatment groups will be performed using Fisher's exact tests. Only p-values  $\leq 0.100$  when rounded to three digits will be presented.

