  9. Systemic use of known strong cytochrome P450 (CYP)3A inhibitors or strong CYP3A inducers from Screening through the end of the study (refer to Table 1 for examples of commonly used strong CYP3A inhibitors and inducers).
  10. Receipt of any live vaccine within 4 weeks prior to the first dose of study drug, or expected need of live vaccination during study participation including at least 4 weeks after the last dose of study drug.
  11. History of any malignancy except for successfully treated NMSC or localized carcinoma in situ of the cervix.
  12. History of clinically significant (per Investigator's judgment) drug or alcohol abuse within the last 6 months.
  13. History of gastrointestinal perforation (other than appendicitis or penetrating injury), diverticulitis or significantly increased risk for GI perforation per investigator judgment.
  14. Conditions that could interfere with drug absorption including but not limited to short bowel syndrome.
  15. Subject has been a previous recipient of an organ transplant.
  16. History of clinically significant medical conditions or any other reason that in the opinion of the Investigator would interfere with the subject's participation in this study or would make the subject an unsuitable candidate to receive study drug.
  17. Active infection(s) requiring treatment with parenteral anti-infectives within 30 days, or oral anti-infectives within 14 days prior the first dose of study drug.

18. History of an allergic reaction or significant sensitivity to constituents of the study drug (and its excipients) and/or other products in the same class.
19. Laboratory values meeting the following criteria within the Screening period prior to the first dose of study drug:
  - Serum aspartate transaminase (AST)  $> 2 \times$  ULN;
  - Serum alanine transaminase (ALT)  $> 2 \times$  ULN;
  - Estimated glomerular filtration rate (GFR) by simplified 4-variable Modification of Diet in Renal Disease (MDRD) formula  $< 40$  mL/min/1.73 m^2;
  - Total white blood cell (WBC) count  $< 2,500/\mu\text{L}$ ;
  - Absolute neutrophil count (ANC)  $< 1,500/\mu\text{L}$ ;
  - Platelet count  $< 100,000/\mu\text{L}$ ;
  - Absolute lymphocyte count  $< 800/\mu\text{L}$ ;
  - Hemoglobin  $< 10$  g/dL.
20. History of any of the following cardiovascular conditions:
  - Moderate to severe congestive heart failure (New York Heart Association class III or IV);

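### The Grade 3 or 4 laboratory flag has no worsening condition, so subjects who enter with lymphocytes of 800 to 900/µL can be counted as on-treatment events without any change

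*SAP*

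**What the plan says.** SAP 10.3.2.3 (Week 12) sets the criterion: "The criteria for potentially clinically significant laboratory values will be determined by OMERACT criteria of Grade 3 or 4", with NCI CTC grades for CPK and creatinine. It adds neither a condition relative to baseline nor the word post-baseline. The percentages are then tested: "Comparisons of the percentage of subjects experiencing a value meeting the criteria between treatment groups will be performed using Fisher's exact tests". P-values are shown only when they are 0.100 or less.

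Protocol 5.2.2, exclusion criterion 19, opens with "Laboratory values meeting the following criteria within the Screening period prior to the first dose of study drug" and removes subjects whose "Absolute lymphocyte count" is below 800/µL. The limit therefore applies to the Screening value, and 800/µL and above is eligible.

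SAP Appendix A gives the bands for Grades 1 to 4 in absolute terms: "K4. Lymphopenia (× 1000) 1.5 – 1.9 1.0 – 1.4 0.5 – 0.9 < 0.5".

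SAP 10.3.3.2 (long-term) uses the treatment groups of SAP 8.1. It says which measurement serves as baseline in each group, with examples for each kind of switch, but not how a value must compare with that baseline to be counted. It also says: "A subject can be counted under different treatment groups if he/she switched treatment and experienced potentially clinically significant laboratory values" under different groups.

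**The concern.** A table of potentially clinically significant values is read as a record of what happened on treatment. A subject who enters at 850/µL and stays there meets the flag on absolute level alone. The count then mixes pre-existing with new abnormality, and the mixture enters the Fisher test.

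Elsewhere the SAP guards against this. Table 10 in SAP 10.4.1 requires a change from baseline for every vital sign, and for blood pressure a threshold as well. Hemoglobin in Appendix A is graded mainly as a fall from the pre-treatment value. The liver criteria in SAP 10.3.2.4 are limited to values after baseline. The lymphocyte flag has none of these conditions.

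At stake are the reported rate of low lymphocyte counts in the long-term tables and the ability of the Week 12 screen to separate arms.

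**Working it through.** **1. Which parameters are affected.** The entry limits in exclusion criterion 19, set against the bands in Appendix A:

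| Parameter | Worst eligible value | Grade at that value |
|---|---|---|
| Lymphocytes | 800/µL | 3 |
| Neutrophils | 1,500/µL | 1 |
| White cells | 2,500/µL | 2 |
| Platelets | 100,000/µL | no worse than 1 |
| ALT, AST | 2 × ULN | 2 |
| Hemoglobin | 10 g/dL | below Grade 3, which by level needs less than 8.0 g/dL |

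Only lymphocytes overlap, in the range 800 to 900/µL. Because the limit is checked at Screening, the Day 1 value may differ. Parameters with no entry limit could also be Grade 3 at baseline; the documents do not say how often.

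**2. How a stable value is counted.** With no comparison rule, a subject at 850/µL throughout meets the Week 12 criterion. In the long-term tables the same subject meets it under the first treatment and can meet it again under the next. The baseline named in 10.3.3.2 does not prevent this, because an absolute band gives the same grade whatever the baseline was.

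**3. Size, as an illustration.** The plan states no figure to reproduce. Inputs:

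- n = 150 per upadacitinib dose, and 75 + 75 = 150 on combined placebo (SAP 4.2).
- Assumed: a share q of each arm is Grade 3 at baseline (5%, range 2 to 10%), and 90% of these are flagged again.
- Assumed: new onset r among the rest is 3% on placebo and 10% on active. No baseline Grade 3 subject moves to Grade 4.
- Assumed: two-sided test at 0.05, since the SAP sets no level for this test.

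Rate without a worsening rule: 0.9q + (1 − q)r. Rate with the rule: (1 − q)r.

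At q = 5%, without the rule:
- placebo 0.045 + 0.95 × 0.03 = 7.35%
- active 0.045 + 0.95 × 0.10 = 14.0%

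With the rule:
- placebo 0.95 × 0.03 = 2.85%
- active 0.95 × 0.10 = 9.5%

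The overstatement is 0.9q = 4.5 points in each arm. The difference is 6.65 points either way, against 7.0 points at q = 0. The ratio is 14.0/7.35 = 1.9 without the rule and 9.5/2.85 = 3.3 with it.

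Exact Fisher power by enumeration:

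| Baseline share q | Without rule | With rule |
|---|---|---|
| 0% | 63% | 63% |
| 2% | 51% | 61% |
| 5% | 40% | 60% |
| 10% | 28% | 56% |

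**4. Other onset rates.** Let 5% of each arm be Grade 3 at baseline and all of them flagged again. Onset of 5% versus 15% gives power of 60% without the rule and 77% with it; 2% versus 10% gives 51% and 78%. The direction is the same and the size depends on the assumptions.

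**The case against.** The strongest reply is that counting every Grade 3 or 4 value is a conservative safety choice, and that the documents already let a reader separate old from new.

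- SAP 10.3.2.2 cross-tabulates baseline grade against maximum grade by arm. This stands for Week 12, but those tables are untested and the Fisher comparison does not use them.
- SAP 10.3.3.2 lists the full course of the parameter for every subject who reaches Grade 3 or 4. This also stands: each case can be inspected. A listing does not correct the percentage in the summary table.
- A worsening rule would miss a fall from 900 to 500/µL, which stays within Grade 3. This is a fair criticism of using the rule alone, and the reason to keep the existing count beside it.
- Period 1 reporting was completed under SAP version 2.0 (SAP 11.1). This stands, and limits the main benefit to tables still to come.

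A reader might also infer more than the documents support:

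- *That laboratory flags in general are inflated by the entry criteria.* Only lymphocytes show the overlap.
- *That the lymphopenia adverse event of special interest is inflated.* Table 8 in SAP 10.2.1.6 identifies it by a company MedDRA query, so this flag does not feed it.
- *That the long-term tables have no control.* SAP 8.1 includes a placebo group, though scheduled placebo treatment ends at Week 12.
- *That shift tables exist for Week 12 only.* The SAP specifies them in its Week 12 section, but Protocol 8.1.5.1 plans safety analyses for both periods combined and includes laboratory shifts.
- *That the long-term analysis ignores baseline.* It defines one; what is missing is the rule for using it.

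**Conclusion.** The gap is real and narrow. The flag in SAP 10.3.2.3 has no worsening condition, and 10.3.3.2 defines a baseline without saying how it enters the count. For lymphocytes, an eligible subject who does not change can be reported as an on-treatment event, possibly under more than one treatment group.

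Given similar baseline shares in the arms, the direction is certain: higher rates, a lower ratio and lower Fisher power, with little change in the absolute difference. The size is not known. The fall to 40% power, against 60% with a rule, rests on an assumed 5% baseline share, 90% repeat flagging and onset of 3% versus 10%; none of these is in the documents. The test is an unadjusted safety screen with no stated power target, so the figures show sensitivity and not a failed design requirement. They do not show that any completed Week 12 conclusion is wrong.

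**What to change.** In SAP 10.3.3.2, for the long-term tables still to be produced, count a subject only if a post-baseline value is Grade 3 or 4 and of a higher grade than the baseline already defined in that section. For 10.3.2.3, produce the same count as a supplementary Week 12 table, labelled as added after Period 1 reporting, and leave the completed analysis as it stands. Keep the any-Grade-3/4 count, the shift tables and the listings alongside.

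The cost is one condition in the derivation and one more set of columns. There are three drawbacks:

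- Worsening within Grade 3 is not counted by the new rule and shows only in the listings and mean-change tables.
- The new rates will differ from earlier tables, so both definitions need clear labels.
- After a switch from 30 mg to 15 mg, 10.3.3.2 keeps the baseline from before the first 30 mg dose. A subject who worsened on 30 mg and stayed at that grade would still be counted under both groups, which a footnote should say.
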